2.2.1. PVP-2016003

Protocol PVP-2016003 is an open-label, uncontrolled Phase 4 Interventional Study of patients who present in hospital/urgent care setting with acquired methemoglobinemia. The population may include pediatric and adult patients (males and females of all ages are included). Eligible patients will receive a single dose of study drug (typically 1 mg/kg of ProvayBlue™) treatment to treat acquired methemoglobinemia resulting in a direct health benefit. Patients will be followed post treatment; safety, efficacy, and PK data will be collected following a predefined data collection schedule (Table 2).

To create a harmonized electronic database, data collected from this study will be entered into the electronic data collection system used for the Observational Study, and the absolute dates of service recorded in this study will be converted to safe-harbor compliant “study days” before data are entered into the database for analyses. In instances where a specific procedure/data collection time was not initially recorded on the paper CRF, a data query will be generated to obtain the specific time from the site. All patients from this protocol are considered as Primary cases.

The original CRFs for Protocol PVP-2016003 requested posttreatment AE tracking, but the Study Procedure Chart indicates that AEs are tracked pretreatment. To be consistent with the Observational Study, any AEs collected prior to study drug treatment will be identified as NOT treatment-emergent events. Non-treatment-emergent AEs will be included in the data listing but will be excluded from data summary (see Section 6.2 for additional details).

Table 2: Study PVP-2016003 Procedures

APPENDIX 2: STUDY FLOW CHART

Data collection/ Assessments	SCREENING/ ENROLLMENT	TREATMENT (Hours after patient presentation)					DISCHARGE	FOLLOW- UP VISIT (Day 5-10) ^b	FOLLOW- UP CALL (Day 10-15) ^b	WITH- DRAWAL
		0	1	2	3	24 ^a				
Informed consent^c	X									
Demographics	X									
Medical history, incl. all concomitant disease(s)	X									
Hospital admission data^d	X									
Methemoglobinemia diagnosis/clinical symptoms	X ^e		X ^f	X ^f	X ^f	X ^f	X ^f	X ^f		X ^f
Inclusion and exclusion criteria	X									
Physical exams^g	X (incl. weight)						X	X		
Vital signs^h	X ⁱ		X ^j	X ^j	X ^j	X	X	X		X
Pregnancy test^j	X									
Methemoglobin	X		X ^k	X ^m	X ⁿ	X	X			X
Hematology^k	X		X	X	X ⁿ	X	X	X		X
Biochemistry^k	X		X	X	X ⁿ	X	X	X		X
12-Lead ECG^o	X					X	X			
ProvayBlue™ Dose 1 administration^p		X								
ProvayBlue™ Dose 2 administration^p			X							
Additional ProvayBlue™ doses administration^p				X	X					
PK sample^q			X	X	X ⁿ	X	X			
Concomitant medications/ medical procedures^r	←	X					→			
Adverse events^s	←	X					→			

a. 24 hours after the end of the infusion of ProvayBlue™ Dose 1.

b. Patients will be followed up with a visit to take place 5 to 10 days following the last ProvayBlue™ administration and a telephone call to take place 10 to 15 days following the last ProvayBlue™ administration.

- c. Due to the nature of the disease indication, the patient's treatment with ProvayBlue™ as per standard of care can take place prior to or after PICD signature. Data collection (retrospective and prospective) for this study and study specific assessments will only take place after PICD signature.
- d. Date, time and initial reason for hospitalization.
- e. Methemoglobinemia diagnosis (including name of toxic agents responsible for methemoglobinemia if available, clinical symptoms related to methemoglobinemia [e.g. sleepiness, cyanosis, dizziness, etc.], methemoglobinemia level at presentation in hospital).
- f. Clinical symptoms related to methemoglobinemia and severity (e.g. sleepiness, cyanosis, dizziness, etc.).
- g. Physical examinations during the study will be based on patient standard of care as appropriate to determine general condition. Weight will be recorded at screening.
- h. Vital signs will include: Systolic (SBP) and diastolic (DBP) blood pressure (mmHg), heart rate (beats per minute [bmp]), body temperature (°C or °F), respiration rate (breaths per minute), oxygen saturation by co-oximetry.
- i. If the patient is treated prior to consent, all available pre-treatment vital sign information should be retrieved where possible;
- j. Within 1 and 2 hours after the end of each ProvayBlue™ infusion (i.e. both Dose 1, Dose 2 and any additional dose if applicable).
- k. Additional (optional) parameters (for example blood gas) will be collected based on available data from patient standard of care.
- l. Within 1 hour after the end of ProvayBlue™ infusion.
- m. If applicable (if the metHb level is acceptable within 1 hour after the end of Dose 1 ProvayBlue™ infusion, the repeat dose of ProvayBlue™ will not be needed).
- n. If applicable, in case of administration of additional doses of ProvayBlue at the discretion of the Investigator
- o. Collection of ECG data is mandatory at admission and approximately at 24 hours after the end of the last ProvayBlue™ infusion or just prior to discharge from the clinic if earlier than 24 hours. The collection of additional data will be based on available 12-lead ECG recordings performed as per patient standard of care as appropriate to determine general condition.
- p. ProvayBlue™ will be administered IV at a dose of 1 mg/kg over 5-30 minutes. If the methemoglobin level remains greater than 30% or if clinical signs and symptoms persist, a repeat dose of 1 mg/kg may be given 1 hour after the first dose. Depending on the clinical status of the patient, additional doses may be administered at the discretion of the Investigator. The data on these additional doses will be recorded in the study CRF.
- q. PK blood samples are to be drawn at the discretion of the Investigator. The suggested schedule of PK blood sampling is:
 - Approximately 1 hour after the end of each ProvayBlue™ infusion (i.e. Dose 1, Dose 2 and any additional dose if applicable);
 - Prior to Dose 2 (or any additional dose) ProvayBlue™ infusion (if applicable);
 - Approximately 24 hours post the end of the last ProvayBlue™ infusion, or just prior to discharge from the clinic if earlier than 24 hours.
- r. Collection of concomitant medications/medical procedures from PICD signature or the start of ProvayBlue™ treatment (whichever occurs sooner) until 10 to 15 days after the last administration of ProvayBlue™;
- s. Collection of AEs that may have occurred since the start of ProvayBlue™ treatment until 10 to 15 days after the last ProvayBlue™ dosing.
- t. All females of childbearing potential will be submitted to a pregnancy test (both urine and serum unless one is not possible) at Screening.

3. DATA POOLING CONSIDERATIONS

A **Data Integration Plan (DIP)** will provide the details of methods to combine the 2 studies into a single database. The following provides the key elements of the DIP.

3.1. Database Structure

It is the intention of Provepharm to enter selected, pertinent CRF data elements from the Interventional Study into the database serving the Observational Study for the purpose of preparing the data summary for PMR-3065-1.

It is therefore expected that certain procedures will have to take place before the CRF data elements from the Interventional Study can be entered into the electronic database. Those procedures include but are not limited to converting the absolute calendar dates from the Investigational Study CRFs to the relative study days used in the database. The integrated datasets will mimic the SDTM structure and naming convention whenever possible.

In study PVP-2016003, PK blood draws were planned and plasma concentration were to be determined. However, PK data are not collected due to poor PK blood sample handling. Therefore, the corresponding dataset (PC) will not be created.

In a situation where a data field that is planned in one protocol but not in the other protocol, the missing data will be marked as 'Not Done' in the database. For instance, the Observational - Study (HQB-METHB-2018001) collects "Patient setting before first presentation", "Diagnosed by", "Diagnosis setting". These 3 questions are not included in the Interventional Study. Hence, data value will be set to 'Not Done' in 'Patient setting before first presentation' dataset XD for patients from the Interventional Study (PVP-2016003).

Table 3: Expected SDTM Domains for the Pooled Database

Name of Data Collection Elements/Form	SDTM Domain
Demographics (age, sex, race, ethnicity)	DM
Weight and height at enrollment	VS
Patient setting before first presentation	XD
Past medical history	MH
Acquired methemoglobinemia diagnosis, including diagnosis ICD-10 Code	XD
Methemoglobinemia assessment and treatment before receiving study drug	XD
Methemoglobinemia signs and symptoms	CE
Co-oximetry before and after ProvayBlue™ treatment	LB
Arterial blood gas	LB
ProvayBlue™ administration	EX
Other treatment for methemoglobinemia	CM
Vital signs	VS
ECG	EG
Hematology, biochemistry, and other labs	LB
Medications and procedures	CM, PR
Hospital course	HO
Adverse events	AE
Follow-up overview and questionnaires	QS

3.2. Analysis Population

The following analysis sets will be identified for data summary.

Enrolled Analysis Set: All patients who sign the informed consent or otherwise meet all local enrollment criteria for the study are considered to have enrolled.

Safety Analysis Set: The safety set will include all enrolled patients who are treated with at least 1 ProvayBlue™ infusion dose. The safety analysis set will be used for safety data summary. Specifically, the safety population will include all treated patients from the Interventional Study and the Observational Study.

Efficacy Analysis Set: The efficacy analysis set includes all safety analysis set patients who have at least 1 metHb assessment before and after ProvayBlue™ infusion and who are Primary cases. This analysis set will be used for efficacy endpoint evaluation.

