8. INVESTIGATIONAL PLAN

8.1. SUMMARY OF STUDY DESIGN

This is an open label, uncontrolled Phase 4 study of 10 patients who present in hospital/urgent care setting with acquired methemoglobinemia. The population may include pediatric and adult patients (males and females of all ages are included).

The aim of the study is to confirm safety and efficacy of ProvayBlueTM for the treatment of acquired methemoglobinemia.

This study comprises of an analysis of data for patients presenting with acquired methemoglobinemia and requiring ProvayBlueTM. The analysis itself will focus on clinical outcome of treatment with ProvayBlueTM alone. If possible, depending on the number of patients, the data will be summarized by age, sex and body weight.

The study will include sites which will be based in France, Germany, UK and the US.

ProvayBlueTM will be administered IV at a dose of 1 mg/kg over 5-30 minutes. If the metHb level remains greater than 30% or if clinical signs and symptoms persist, a repeat dose of 1 mg/kg may be given 1 hour after the first dose.

Depending on the clinical status of the patient, additional doses may be administered at the discretion of the Investigator. The data on these additional doses will be recorded in the study Case Report Form (CRF).

[figure not shown]
Due to the nature of the disease and indication, the patient's treatment with ProvayBlueTM may take place per the Investigator's standard of care prior to or after Patient Informed Consent Document (PICD) signature. Data collection (retrospective and prospective) for this study and study specific assessments will only take place after PICD signature.

Safety will be monitored throughout the study by repeated clinical and laboratory evaluations according to protocol requirements.

The expected duration of the study will vary for each patient depending on the clinical situation and outcome of treatment. Patients will be followed-up 5 to 10 days (follow-up visit), and 10 to 15 days (follow-up call) after the last administration of ProvayBlueTM. End of study is defined as the Last Patient Last Visit (LPLV).

The study design is summarized in Figure 8-1.

Figure 8-1: Study Design

A schedule for the tests and evaluations to be conducted in this study is found in the flow chart in APPENDIX 2:Study Flow Chart.

The study duration of the trial will vary for each patient depending on the clinical situation and outcome of treatment.

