3.3. Endpoints

3.3.1. Efficacy Endpoints

The efficacy data summary will include the following endpoints:

- 1) Change from baseline in metHb after the first dose of ProvayBlue™ infusion.
The primary efficacy will be the number (%) patients with $\geq 50\%$ reduction in metHb based on the first available posttreatment assessment.
 - The following are secondary endpoints to support the primary endpoint.
 - i. Change in metHb posttreatment over time
 - ii. Time when 50% reduction in metHb is observed for the first time.
- 2) Change from baseline in vital signs (blood pressure, respiratory rate, and heart rate) after the first dose of ProvayBlue™ infusion.
 - The secondary efficacy will be the number (%) of patients with concomitant normalization of vital signs within 2 hours, inclusive, after the end of infusion of the first dose of ProvayBlue™
 - Time (hours) when the first incidence of normal vital signs was observed in patients who had abnormal baseline vital signs
- 3) In addition, 13 prespecified clinical signs and symptoms associated with methemoglobinemia and their intensity (as National Cancer Institute Common Terminology Criteria for Adverse Events [NCI-CTCAE] grade) before and after ProvayBlue™ treatment are collected. The presence/absence of those signs and symptoms will be treated as an 'other' efficacy endpoint since decrease and/or resolution of those signs and symptoms may be considered supportive of efficacy.

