4. DATA SUMMARIES

It is anticipated that the pooled results will be presented as a series of individual patient descriptive narratives with limited statistical analysis. The narratives will also identify issues in individual patient past medical history, exposures, and comorbidities that may impact the consideration and interpretation of “normal” vital signs and related parameters.

When appropriate, summary tables will also be prepared that will include descriptive statistics, such as sample size, mean, standard deviation, minimum, median, and maximum for continuous variables and number (%) of patients for categorical variables. Data summaries will provide descriptive statistics for all patients, patients with possible causative agent of Dapsone, and patients with non-Dapsone causative agents.

All data in the pooled database will have a patient level data listing.

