4.2. Demographics and Baseline Characteristics

The demographic summary will include descriptive statistics for age, sex, race, ethnicity, weight, height, and body mass index (BMI) at baseline.

Baseline characteristics and patient population characteristics will also include the following study information:

- 1) Patient setting before first presentation
- 2) Acquired methemoglobinemia diagnosis:
 - a. Diagnosis by
 - b. Diagnosis setting
 - c. Suspected causative agent
 - d. Exposure to agent
- 3) Methemoglobinemia assessments and treatment at baseline:
 - a. Any signs and symptoms judged to be clinically associated with the acquired methemoglobinemia (yes/no)?
 - b. Are co-oximetry results available from the index hospitalization (yes/no)?

- c. Are arterial blood gas results available from the index hospitalization (yes/no)?
- d. Baseline metHb level
- e. Was ProvayBlue™ administered before enrollment to the study (yes /no)?
- f. Were any other treatments employed to mitigate the acquired methemoglobinemia (yes/no)?

Demographics and baseline characteristics will be tabulated for the safety analysis set (Tables 14.1.2.1 and 14.1.2.2) and efficacy analysis set (Table 14.1.2.3) with no formal inferential tests. Demographic data will be provided as a data listing (Listing 16.2.2).

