4.6. Prior and Concomitant Medications

All prior and concomitant medications will be listed without any formal summaries (Listing 16.2.6).

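### No efficacy table separates patients who also received other methemoglobinemia treatment, although the protocol says the analysis focuses on ProvayBlue alone

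*SAP*

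**What the plan says.** - **Focus.** Protocol 8.1, and the synopsis in the same words: "The analysis itself will focus on clinical outcome of treatment with ProvayBlueTM alone".
- **Efficacy set.** SAP 3.2: "The efficacy analysis set includes all safety analysis set patients who have at least 1 metHb assessment before and after ProvayBlue™ infusion and who are" labelled Primary. SAP 3.7.3 repeats the rule. Other treatment is not mentioned in either place.
- **Grouping.** SAP 4: "Data summaries will provide descriptive statistics for all patients, patients with possible causative agent of Dapsone, and patients with non-Dapsone causative agents". No other split of the efficacy results is planned. SAP 7.1 assigns Tables 14.2.1.1, 14.2.1.2 and 14.2.2.1 to the efficacy set.
- **What is recorded.** SAP 3.1, Table 3, lists "Other treatment for methemoglobinemia" in the concomitant-medication domain, and a separate element covers assessment and treatment before study drug. Among the baseline items in SAP 4.2 is: "Were any other treatments employed to mitigate the acquired methemoglobinemia (yes/no". Table 14.1.2.3 tabulates these items for the efficacy set.
- **What is done with it.** SAP 4.6: "All prior and concomitant medications will be listed without any formal summaries".
- **Timing of the outcome.** In SAP 3.3.1 the primary measure is a metHb fall of at least 50% "based on the first available posttreatment assessment". SAP 5.1.1 accepts that this assay may come hours after the infusion. Vital signs are judged within 2 hours of the end of the first infusion.

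**The concern.** Neither study has a control arm. The case for the drug rests on what happens to metHb, vital signs and symptoms after the infusion. If another treatment for methemoglobinemia started before or with the infusion, or between the infusion and the reading that is counted, a response cannot be assigned to ProvayBlue.

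The SAP treats such use as a real possibility, because it gives it a data element and a baseline question. The registry took real-world cases without restriction (SAP 1), and Protocol 11 leaves further interventions to the investigator's discretion. Where the first metHb is drawn late, there is more time for something else to have been given. SAP 3.7.2 already separates dapsone cases because continuing metHb production affects the result. It makes no comparable provision for a second treatment.

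At stake is whether the report can give any efficacy figure that matches the protocol's stated focus.

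**Working it through.** **1. The two documents side by side**

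| Question | Protocol | SAP |
|---|---|---|
| Is ProvayBlue alone the focus? | Yes, in the synopsis and 8.1 | Not repeated in the objectives (Table 1) or in 3.2 |
| Does the efficacy set depend on other treatment? | No (16.2.2: all enrolled) | No (3.2, 3.7.3) |
| Is there an efficacy result by other treatment? | None planned | None planned; only all / dapsone / non-dapsone (4) |
| Is other treatment recorded? | Concomitant therapy and procedures (11.1) | Table 3 data elements; yes/no item (4.2) |

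The SAP's precedence clause (section 1) covers the statistical section of the protocols. The focus statement is in the synopsis and the design section, so the clause does not clearly remove it.

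**2. What can be sized**

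The plan gives no figure for co-treated patients, so there is none to reproduce. The inputs it does give are 7 enrolled in PVP-2016003 and 24 in the registry (SAP 1), so the efficacy set has at most 7 + 24 = 31 patients. The number of Primary cases is not stated.

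**3. Illustration**

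Assumptions: n patients in the set; x responders, about 90%; k co-treated patients, all responders; exact (Clopper-Pearson) 95% intervals, since the SAP names no method.

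- As planned: x/n
- Co-treated excluded: (x − k)/(n − k)
- Co-treated counted as non-responders: (x − k)/n

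| n | k | As planned | Excluded | Non-responders |
|---|---|---|---|---|
| 10 | 2 | 9/10 = 90% (55.5 to 99.7) | 7/8 = 87.5% (47.3 to 99.7) | 7/10 = 70% (34.8 to 93.3) |
| 20 | 2 | 18/20 = 90% (68.3 to 98.8) | 16/18 = 88.9% (65.3 to 98.6) | 16/20 = 80% (56.3 to 94.3) |
| 20 | 4 | 18/20 = 90% (68.3 to 98.8) | 14/16 = 87.5% (61.7 to 98.4) | 14/20 = 70% (45.7 to 88.1) |
| 31 | 6 | 28/31 = 90.3% (74.2 to 98.0) | 22/25 = 88.0% (68.8 to 97.5) | 22/31 = 71.0% (52.0 to 85.8) |

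For n = 20 and k = 2, exclusion moves the rate by 90 − 88.9 = 1.1 points and counting as non-response by 90 − 80 = 10 points. How co-treated patients are handled therefore matters more than the fact that they are present.

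**4. Why timing decides the handling**

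With n = 20 and k = 2:

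- If both treatments began before or with the infusion, restricting the set gives 16/18, and nobody remains to be recoded.
- If both began after the infusion but before the counted reading, the restricted set is still 18/20, and recoding gives 16/20.
- With one of each, the restricted set gives 17/19 = 89.5%, and recoding gives 16/19 = 84.2%.

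Now suppose that the two co-treated patients were the two non-responders, given something else because they did poorly after the infusion. Dropping them turns 18/20 = 90% into 18/18 = 100%. Counting them as non-responders leaves 90%. Excluding patients for treatment given after the infusion can therefore raise the rate artificially.

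**The case against.** The strongest reply is that the SAP breaks no rule. The word alone does not appear in the objectives (Protocol 7.1), the endpoints (7.2), the full analysis set (16.2.2) or the evaluability definition (9.5.2). In a single-product, uncontrolled study it may mean only that there is no comparator. This stands in part. The statement is one of focus, and a reader who infers that the SAP violates a formal population definition goes further than the text. But neither document ever put the focus into operation, and that is the gap.

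The second reply is that nothing shows that anyone was co-treated. This stands. A reader might infer that the tables do credit ProvayBlue with responses to other treatments. The documents show only that the question was asked and that such patients would not be separated.

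The third reply is that the information will be visible: a count in Table 14.1.2.3, medications and procedures in Listings 16.2.6 and 16.2.7, individual profiles, and narratives for at most 31 patients. This is real mitigation, and it means that the responder rate is not the whole efficacy case. But the count does not say who responded or when the other treatment began. SAP 4 commits the narratives to medical history, exposures and comorbidities, and does not name other treatments.

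**Conclusion.** The point holds as a gap in reporting. The protocol announces a focus on ProvayBlue alone, the data needed to look at it are at least partly planned, and no efficacy result uses them. Any bias is possible and unquantified, because the number of co-treated patients and the number of Primary cases are both missing from the documents.

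Two stronger conclusions should not be drawn. First, a shift of 5 or 10 points for one or two patients in a set of 20 arises only if co-treated responders are recoded as non-responders. If they are removed, two such patients move the rate by 1.1 points. Second, a row that drops every co-treated patient should not be presented as the answer to the protocol's question, because treatment given after the infusion may mark poor responders.

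All rates above rest on the assumed n, x and k and on exact intervals. A low-cost sensitivity analysis is warranted; a new main analysis is not.

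**What to change.** Keep the SAP 3.2 efficacy set for the main result and describe it as ProvayBlue with or without other methemoglobinemia treatment. To Tables 14.2.1.1, 14.2.1.2 and 14.2.2.1 add two sensitivity rows, each with a 95% confidence interval:

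- **(a)** responders among patients with no other methemoglobinemia treatment started before or with the first infusion;
- **(b)** the same patients, with those whose other treatment started after the infusion but before the assessment used counted as non-responders and kept in the denominator.

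State what the assessment used is in each table: the first post-infusion metHb for the two metHb tables, and the readings in the 2-hour window for vital signs.

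Take start times from the concomitant-medication and procedure records. The yes/no item carries no timing. It may also be set to Not Done for PVP-2016003: SAP 3.1 does this for fields that one protocol lacks, and Protocol 12.1 and 12.2 show no dedicated item. Before the tables are run, define which treatments count as other treatment and how a record without a start time is classed.

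The cost is some SAP wording and two rows per table, from records already planned for the database, plus queries where times are missing. Row (a) has fewer patients and a wider interval if anyone is removed, and row (b) may show a less favourable rate. If nobody was co-treated, all rows coincide and the question is closed.
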